5.2 Handling Missing Data

Missing data will be handled as follows:

• For prior systemic cancer therapies and medical history of cancer, the study day corresponding to the start and stop date of the regimen will be calculated when calculating duration of the therapy/history and relevant time to the first study dose, etc. For partially missing start dates, missing day of the month will be imputed as the first of the month and missing month will be imputed as January. For partially missing stop dates, missing day of the month will be imputed as the last day of the month and missing month will be imputed as December and at least 1 day after the start date. No imputation will be done if the year is missing.

For the duration of AEs, AE start date with missing month and year and AE stop date with missing year will not be imputed.

In general, no imputation will be considered for missing date or partial dates with the following exceptions:

- For duration of AEs, partially missing dates for start of AE, will be imputed as follows:
 - Start day of AE is missing
 - If the reported month of occurrence of the AE is after the study dose, then day will be imputed as the first day of the month of occurrence of AE.
 - If the reported month of occurrence of the AE is the current month as the dose, then the missing day will be imputed as the same day as study dose date.
- For duration of AEs, a partially missing stop date of the AE will be imputed as follows:
 - o If the month is missing, but year is present, either 31st December, the date of discontinuation from the study, or the date of death, whichever is earlier, will be used as the stop date.
 - If the day is missing, but year and month are present, either the last day of that month, the date of discontinuation from the study, or the date of death, whichever is earlier, will be used as the stop date.

Some laboratory analytes may be reported by range (e.g., gamma-glutamyl transferase [GGT] < 17 U/L) and will be imputed by the corresponding boundary (e.g., 17 U/L).

6.0 ANALYSIS POPULATIONS

Screened patients: All patients who signed study participation informed consent.

Enrolled patients: All patients who are assigned/randomized to either the bempegaldesleukin/SOC or placebo/SOC treatment groups.

Safety/Treated Population: All patients who receive at least 1 dose (full or partial dose) of study drug.

Pharmacokinetic Population: All patients in the Safety Population with at least one measurable concentration.

Immunogenicity Population: All patients in the Treated Population with at least baseline and one post-baseline ADA assessment.

7.0 STATISTICAL ANALYSIS

7.1 Subject Disposition

Subject disposition information will be summarized for all patients. Summaries will include: the number and percentage of patients in each analysis population, the number and percentage of patients who completed the study, and the number and percentage of patients who discontinued the study and the reason for discontinuation. All patients randomized/enrolled in the study will be included in the summary table.

7.2 Important Protocol Deviations

Important protocol deviations are a subset of the protocol deviations that may significantly impact the completeness, accuracy, and/or reliability of the study data or that may significantly affect a patient's rights, safety, or well-being.

Final list of the important protocol deviations and the associated categories will be determined by the study team before the database lock.

The number and percentage of patients in each important protocol deviations category and subcategory will be summarized by treatment group and total. All protocol deviations will be listed.

7.3 Demographic and Baseline Characteristics

Demographic variables include age, sex, ethnicity, and race. Other baseline characteristics include height, weight, calculated body mass index (BMI), and vital signs. Demographic and baseline characteristics will be summarized for the Treated Population.

Age will be calculated as:

Integer [(Date informed consent signed – Date of birth) / 365.25].

BMI will be calculated as:

Weight (kg) / Height (m²).

7.4 Prior and Concomitant Medications and Procedures

Prior and concomitant medications will be coded to ATC level and preferred drug name using WHO-DDE.

Prior medications are defined as medications taken starting prior to the first dose. Prior medications will be summarized for the Treated Population using the same analytical procedures as concomitant medications. Concomitant medications are defined as medications taken on or after the date of first study dose, including medications initiated prior to the date of first dose and continued during treatment, and medications initiated on or after the date of first dose, but before the last study dose + 30 days or start of subsequent anticancer therapy, whichever is earlier.

Concomitant medications will be tabulated for the Treated Population by WHO-DDE ATCL-2 classifications and preferred term. If the ATCL-2 classifications is missing, the next non-missing higher level of classification will be used (Level 1). If a patient reports the same medication multiple times, then the frequency reported for that medication will be incremented by only one. As with the medication, if a patient reports multiple medications within the same ATCL-2 classification then the frequency for that ATCL-2 classification will be incremented by only one. Percentages will be calculated using the total number of patients in the Treated Population.

Prior and concomitant medications will also be presented in a data listing.

7.5 Study Treatment Exposure

Total dose administered (mg, mg/kg) will be summarized by N (observed), mean, SD, median, Q1, Q3, min, and max for each bempegaldesleukin dose level in Treated Population. Number and percentage of patients with full dose will be provided for each bempegaldesleukin dose level and total in the Treated Population.

7.6 Efficacy Analyses

7.6.1 Analysis of Percentage of Patients Who Require Supplemental Oxygen

Number and percentage of patients who require supplemental oxygen will be provided by treatment group and total for Treated Population.

7.6.2 Analysis of Shift from Baseline to Post-Baseline in Clinical Status

Shift from baseline to post-baseline clinical status based on the World Health Organization (WHO) Clinical Progression Scale will be provided for patients with no change, with 1, 2, and ≥3 points of improvement or worsening in the Treated Population. The 10-point WHO Clinical Progression Scale is as follows:

Patient state	Descriptor	Score
Uninfected	Uninfected; no viral RNA detected	0
Ambulatory mild	Asymptomatic; viral RNA detected	1
disease	Symptomatic; independent	2
	Symptomatic; assistance needed	3
Hospitalized: Moderate	Hospitalized, no oxygen therapy ^a	4
disease	Hospitalized; oxygen by mask or nasal prongs	5
Hospitalized: Severe	Hospitalized; oxygen by non-invasive ventilation or high-flow	6
disease	Intubation and mechanical ventilation, $PaO_2/FiO_2 \ge 150$ or $SpO_2/FiO_2 \ge 200$	7
	Mechanical ventilation, PaO ₂ /FiO ₂ < 150 (SpO ₂ /FiO ₂ < 200) or vasopressors	8
	Mechanical ventilation, $PaO_2/FiO_2 < 150$ and vasopressors, dialysis, or ECMO	9
Dead	Death	10

Abbreviations: ECMO = extracorporeal membrane oxygenation; FiO_2 = fraction of inspired oxygen; PaO_2 = partial pressure of arterial oxygen; SpO_2 = oxygen saturation

Source: WHO 2020

7.6.3 Analysis of Clinical Status Based on the WHO Clinical Progression Scale on Days 3, 5, 8

Number and percentage of patients will be provided for each clinical status (i.e. WHO progression scale point) on Days 3, 5, and 8 by treatment group and total.

7.6.4 Analysis of Number of Days Receiving Supplemental O₂, Non-Invasive, High-Flow, Mechanical Ventilation, ECMO

Oxygen days are defined as days where the clinical status score is equal to 5, 6, 7, 8, or 9. The total number of oxygen days is the sum of all reported oxygen days.

Number of oxygen days will be summarized by N (observed), mean, SD, median, Q1, Q3, min, and max for each treatment group and total in Treated Population. Number and percentage of

a. If hospitalized for isolation only, record status as for ambulatory patient.

patients will be provided for number of oxygen days by treatment group and total in Treated Population, if deemed necessary.

9.0 PHARMACOKINETIC ANALYSES

Listings for blood collection dates, times and concentrations will be generated by patient for each analyte. Sampling time deviations will be computed as differences between scheduled (nominal) and actual sampling times and expressed in hours and as a percentage of the nominal time.

Observed plasma NKTR-214-RC (bempegaldesleukin-related molecules; mixture of compounds containing IL-2 independent of PEG conjugation status) at each nominal PK sampling time will be tabulated using descriptive statistics, including but not limited to N (number of non-missing data), N (missing), arithmetic mean, standard deviation (SD), standard error of the mean (SEM), arithmetic coefficient of variation (CV%), geometric mean, geometric CV%, median, minimum, and maximum.

Individual and overlay plots of observed plasma NKTR-214-RC concentration-time profiles will be generated on linear and semi-logarithmic scales using actual times.

Plots of mean (+ standard deviation) observed plasma NKTR-214-RC concentrations versus nominal time will be generated on linear and semi-logarithmic scales based on nominal sampling times.

PK samples that were collected outside the protocol accepted time windows will be excluded from summary tables and summary figures.

The PK analyses will use Quality Assured (QA) final bioanalytical data. Missing concentration values will not be imputed. When summarizing concentrations, zero values will be excluded from the calculation of geometric means and CV% geometric mean, however, they will be included for all other summary statistics and the number of non-zero concentrations will be reported. Missing values for any PK parameters will not be imputed and will be handled as missing.

When calculating PK parameters, all Cycle 1 pre-dose concentrations that are below the limit of quantification (BLQ) will be set to 0; all other concentrations that are BLQ will be set to missing for calculation of PK parameters and will be set to 0 for summary statistics.

PK parameters will be derived by Phoenix WinNonlin (version 8.3 or higher) based on noncompartmental (NCA) methods. PK parameters (Error! Reference source not found.) will include C_{max} , T_{max} , AUC_{last} , AUC_{inf} , V_z , CL, and $t_{1/2}$ for NKTR-214-RC. Time zero will be

defined as the start time of the infusion. Linear-up/log-down NCA methods will be used to estimate AUC.

NCA PK parameters listed in

Table 2: will only be derived when all specified requirements are met. Where requirements are not met, PK parameter values will be reported as "not determinable".

Table 1: Pharmacokinetic Parameter Definitions

PK Parameter	Description
AUC _{inf}	Area under the concentration-time curve calculated from time 0 to infinity
AUC _{last}	Area under the concentration-time curve calculated from time 0 to the last measurable concentration
AUC _{0-96h}	Area under the concentration-time curve calculated from time 0 to 96 hours after dosing
AUC _{0-168h}	Area under the concentration-time curve calculated from time 0 to 168 hours after dosing
CL	Systemic clearance
C _{max}	Maximum observed concentration following study drug administration
t _{1/2}	Half-life: the time required for the concentration to reach half of its original value
T _{max}	Time to reach maximum concentration
V_z	Volume of distribution during the terminal elimination phase following intravenous administration

Table 2: Noncompartmental Analysis Requirements

PK Parameter	Requirement				
	A minimum of 3 time points should be used for determining lambda_z, not including the C _{max} time point.				
$t_{1/2}$, AUC $_{inf}$, CL, V_z	The span of the terminal phase must be at least 2 times the half-life for lambda_z to be determined.				
	Where Rsq_adj < 0.75, lambda_z will not be determined				
	If lambda_z is not determined then t _{1/2} , AUC _{inf} , CL, or V _z will not be reported.				
AUC _{inf}	The extrapolated area should not contribute more than 20% to the total AUC_{inf} for the estimation of AUC_{inf}				

PK parameters will be listed by patient and summarized using descriptive statistics, including but not limited to N (observed), geometric mean, mean, SEM, SD, CV%, geometric CV%, median, minimum and maximum. PK parameters will be summarized for each treatment group. T_{max} , CL, $t_{1/2}$, and V_z will also be summarized in total Treated Population.

Rounding for the reporting of PK parameters will be to three significant digits. Percentages such as CV% presented in tables will be rounded to one decimal place. The same convention will be followed for descriptive statistics, except for n, which will be rounded to the whole value.

10.0 IMMUNOGENICITY ANALYSES

10.1 Immunogenicity

Validated methods to detect anti-bempegaldesleukin, anti-PEG and anti-IL-2 anti-drug antibodies (ADA) will be used to analyze immunogenicity samples. Serum samples will be analyzed by multi-tiered ADA testing as per the 2019 FDA guidance (FDA 2019). Immunogenicity sample testing will be done in tiers. Samples will be first tested with screening electrochemiluminescence assays (ECLA). Putative positive samples for antibempegaldesleukin or anti-IL-2 antibodies will then be analyzed in competition ECLA to confirm positivity. Confirmed anti-bempegaldesleukin antibodies-positive samples will be tested further in a polyethylene glycol (PEG) immuno-competition assay to determine the antibody specificity of the reactivity to the PEG or non-PEG (IL-2, linker) moiety of bempegaldesleukin. Confirmed positive samples from each assay (anti-bempegaldesleukin and anti-IL-2) will then be tested to obtain a titer. Samples confirmed to be positive for anti-bempegaldesleukin and anti-IL-2 antibodies will also be tested for neutralizing activity for IL-2 using a validated cell-based assay. The data will be summarized for anti-bempegaldesleukin, anti-PEG, anti-IL-2 antibodies and will be reported by sample and patient status.

For sample status, immunogenicity data will be summarized by the number and percentage of confirmed anti-drug antibodies (ADA) to bempegaldesleukin, PEG, IL-2 by analyte and visit. The samples will be classified as baseline ADA-positive, if ADA is detected in the immunogenicity sample collected before initiation of the treatment and baseline ADA-negative, if ADA is not detected in the immunogenicity sample collected before initiation of the treatment. ADA samples will be classified as positive if after initiation of the treatment, the ADA is detected in a sample from a subject who was baseline negative, or if there is at least 4-fold or greater (\geq) increase in ADA titer in comparison to the baseline positive titer.

For patient status, immunogenicity will be reported by summarizing the number and percentage of ADA-positive patients and ADA-negative patients at baseline and after drug administration with positive status of anti-bempegaldesleukin, anti-PEG, anti-IL-2 ADA. In the immunogenicity evaluable population, the patients will be classified as treatment-induced ADA-positive if they were ADA-negative at baseline and became ADA-positive at any time after starting the treatment, or if they were ADA-positive at baseline and had a post-baseline ADA-positive titer that was at least 4-fold or greater (\geq) than baseline positive titer (Treatment-boosted). Treatment-emergent ADA-positive patients will be the sum of treatment-induced and treatment-boosted ADA-positive patients. Patients with at least one ADA-positive sample with neutralizing activity will be classified as neutralizing positive. All other ADA-evaluable patients are considered as treatment-emergent ADA negative.

10.2 Safety Evaluation of ADA

All patients with ADA as mentioned above will be assessed for infusion related reactions (including hypersensitivity/angioedema/anaphylaxis) and will be compared against ADA negative patients.

10.3 Definitions

There are two sets of definitions: one for categorizing individual samples in Table 3 and another for categorizing patient responses in Table 4.

Table 3: ADA Status: Individual Samples

ADA Status	Definition			
Baseline Negative	ADA is not detected in the last sample before initiation of treatment			
Baseline positive	ADA is detected in the last sample before initiation of treatment			
Anti-bempegaldesleukin ADA-positive sample	After initiation of treatment, (1) an ADA detected (positive seroconversion) sample in a patient for whom anti- bempegaldesleukin ADA is not detected at baseline, or (2) an ADA detected sample with anti-bempegaldesleukin titer to be at least 4-fold or greater (≥) than baseline positive titer			
Anti-PEG ADA-positive sample	Sample with a positive result in PEG -specificity assay.			
Anti-IL-2 ADA-positive sample	After initiation of treatment, (1) an ADA detected (positive seroconversion) sample in a patient for whom anti-IL-2 ADA is not detected at baseline, or (2) an ADA detected sample with anti-IL-2 titer to be at least 4-fold or greater (≥) than baseline positive titer			

Table 4: ADA Response Categories: Patient Level

ADA status	Description		
Baseline ADA-positive	A patient with baseline ADA-positive sample		
ADA-Negative Patient	Patient with no ADA-positive sample after the initiation of treatment.		
	Note: due to the definition of an ADA positive sample for a patient testing positive at baseline (see sample status table, above), it is possible (but highly unlikely) for a patient with a stable anti-drug titer throughout the study to be classified as 'ADA-negative'		
ADA-Positive Patient (Treatment-Emergent positive)	Patient with at least 1 ADA positive-sample (relative to baseline) at any time after initiation of treatment		
Neutralizing positive	At least 1 ADA-positive sample with neutralizing antibodies detected		

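### The SAP has two conflicting rules for anti-PEG positivity: Table 3 ignores baseline, while section 10.1 relies on a titre that is not planned for PEG

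*SAP*

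**What the plan says.** Four parts of the SAP bear on this point.

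- **Table 3 (SAP 10.3), sample level.** The anti-PEG row reads, in full, "Sample with a positive result in PEG -specificity assay". The anti-bempegaldesleukin row applies only after treatment has started. It asks for seroconversion from a negative baseline, or "an ADA detected sample with anti-bempegaldesleukin titer to be at least 4-fold or greater" than the baseline positive titre. The anti-IL-2 row has the same form.
- **SAP 10.1, assay tiers.** "Confirmed anti-bempegaldesleukin antibodies-positive samples will be tested further in a polyethylene glycol (PEG) immuno-competition assay", so the PEG assay is a follow-on test for specificity. Titres are planned as follows: "Confirmed positive samples from each assay (anti-bempegaldesleukin and anti-IL-2) will then be tested to obtain a titer". Protocol 5.10 agrees, and neither document plans a PEG titre.
- **SAP 10.1, reporting rules.** Sample results are tabulated as "number and percentage of confirmed anti-drug antibodies (ADA) to bempegaldesleukin, PEG, IL-2 by analyte and visit". The same paragraph then gives a rule that is not limited to one analyte. After treatment starts, a sample is positive if "the ADA is detected in a sample from a subject who was baseline negative, or if there is at least 4-fold or greater" rise over the baseline positive titre. The next paragraph, which names anti-PEG, applies this logic to patients. They are "classified as treatment-induced ADA-positive if they were ADA-negative at baseline and became ADA-positive at any time after starting the treatment", or boosted if the titre rises at least 4-fold.
- **Table 4 (SAP 10.3), patient level.** A treatment-emergent positive is a "Patient with at least 1 ADA positive-sample (relative to baseline) at any time after initiation of treatment".

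**The concern.** The anti-PEG row lacks the three conditions that its neighbours carry: a post-treatment sample, a comparison with baseline, and a titre rise where baseline was positive. A programmer who follows the analyte-specific row will flag every post-dose sample that is PEG-specific, including those from patients whose antibody was there before dosing and has not changed. A programmer who follows 10.1 will not flag them. The SAP ranks neither rule above the other, so the same data could give two different anti-PEG tables.

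The 10.1 rule does not fully settle the matter either. Its second branch needs a titre, and none exists for PEG. At stake are how anti-PEG rates are read beside the other two antibodies, and who counts as ADA-negative when infusion reactions are compared under SAP 10.2.

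**Working it through.** The plan gives no figure to reproduce here, so the check sets the rules side by side and applies them to four kinds of patient.

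| Patient | Table 3 anti-PEG row, post-dose sample | SAP 10.1 rule |
|---|---|---|
| A. No antibody at baseline; PEG-specific after dosing | Positive | Positive (newly detected) |
| B. PEG-specific at baseline and after dosing, titre unchanged | Positive | Not positive |
| C. PEG-specific at baseline and after dosing, anti-bempegaldesleukin titre up at least 4-fold | Positive | Not determinable: no PEG titre, and no statement that the anti-bempegaldesleukin titre stands in |
| D. Anti-bempegaldesleukin positive but not PEG-specific at baseline; PEG-specific after dosing, titre rise below 4-fold | Positive | Depends on whether a negative baseline means negative for PEG or for any ADA |

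The rules agree only on A. Patient D arises because the baseline rows of Table 3 do not name an analyte.

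Patient B also falls between the categories of Table 4. Under the Table 3 anti-PEG row, B has a positive sample after dosing and so is not an ADA-negative patient. B is not positive relative to baseline either. The end of SAP 10.1 classes every remaining evaluable patient as treatment-emergent negative. The note in Table 4 accepts that a patient with a stable titre may be classed as negative because of the sample definitions, but the anti-PEG row lacks the condition that would produce that result.

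**Is a surrogate titre available?** Yes. Only confirmed anti-bempegaldesleukin positives enter the PEG assay, and confirmed positives in the anti-bempegaldesleukin assay are titred. Every PEG-specific sample should therefore already have an anti-bempegaldesleukin titre.

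**Illustration of size (prevalence assumed).** SAP 3.0 and 4.0 plan 3 cohorts with 5 patients on drug in each, so n = 3 × 5 = 15. Let p be the share with anti-PEG antibody at baseline. Suppose the antibody persists after dosing and the Table 3 row governs. The expected number like patient B is n × p, and the chance of at least one is 1 − (1 − p)^15.

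- p = 2%: 15 × 0.02 = 0.3; 1 − 0.98^15 = 26%
- p = 5%: 15 × 0.05 = 0.75; 1 − 0.95^15 = 54%
- p = 10%: 15 × 0.10 = 1.5; 1 − 0.90^15 = 79%
- p = 20%: 15 × 0.20 = 3.0; 1 − 0.80^15 = 96%

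The same expectation applies to the 15 placebo patients. If 10.1 governs, the number is 0 at every p.

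**The case against.** The strongest reply is that the SAP already excludes stable antibody. The general sample rule in 10.1 sits in the paragraph that lists PEG among the analytes, the patient rule follows in a paragraph that names anti-PEG, and Table 4 compares with baseline. On that view the Table 3 row is merely abbreviated. This stands to a large extent. A reader of Table 3 might infer that the trial will report pre-existing anti-PEG antibody as a treatment effect, and that anti-PEG incidence will be inflated. The documents do not support that as a settled consequence, because three other rules point the other way. What remains is an unresolved conflict and a rise branch with no stated titre.

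A second reply is that baseline anti-PEG status will not be hidden. That is right: SAP 10.1 already plans results by analyte and visit, and patient counts at baseline and after dosing.

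A third concerns SAP 10.2. A reader might infer that pre-existing antibody contaminates the infusion-reaction comparison. The documents do not bear this out. There is one infusion, on Day 1, and ADA samples are scheduled predose, on Day 8 and at follow-up. For a reaction during the infusion, baseline antibody is the status that can precede it. Moving stable baseline-positive patients into the ADA-negative group would make that comparison worse.

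**Conclusion.** The point holds as a conflict between rules. Table 3 as written labels a post-dose sample with stable, pre-existing anti-PEG antibody as positive; SAP 10.1 and Table 4 would not; and the SAP does not say which prevails. Where 10.1 is followed, a boosted anti-PEG response in a baseline-positive patient cannot be determined from the text.

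The size is unknown. The documents give no baseline prevalence, and the illustrative counts rest on an assumed prevalence, persistence of antibody, three full cohorts, and Table 3 governing. The effect is confined to descriptive immunogenicity tables, including the SAP 10.2 display. The DLT definition, the escalation rule and the sample size do not use ADA status. This is a minor point that is cheap to settle before unblinding.

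**What to change.** Align the Table 3 anti-PEG row with SAP 10.1. Define a treatment-emergent anti-PEG positive as either:

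1. a PEG-specific positive sample after treatment starts, in a patient who was PEG-negative at baseline; or
2. in a patient who was PEG-positive at baseline, a PEG-specific sample after treatment starts whose anti-bempegaldesleukin titre is at least 4 times the baseline titre.

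State that the titre in (2) is a surrogate that may also reflect reactivity to the non-PEG part of the molecule. Define baseline status separately for each analyte. In the SAP 10.2 comparison, show baseline-positive patients as their own group and not within the ADA-negative group.

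The cost is SAP wording and one more table row. No new assay is needed, because the titres are already planned. The drawback is reliance on a surrogate titre in baseline-positive patients.
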